6.2 Safety/Tolerability

Analyses will be performed for all subjects having received at least one fraction of radiation. The study will use the CTCAE version 5.0 for reporting of adverse events. https://ctep.cancer.gov/protocolDevelopment/electronic_applications/ctc.htm

7.0 ADVERSE EVENTS

7.1 Adverse Event Monitoring

Adverse event data collection and reporting, which are required as part of every clinical trial, are done to ensure the safety of subjects enrolled in the studies as well as those who will enroll in future studies. Adverse events are reported in a routine manner at

scheduled times during a trial. Additionally, certain adverse events must be reported in an expedited manner to allow for optimal monitoring of subject safety and care.

All subjects experiencing an adverse event, regardless of its relationship to study therapy, will be monitored until:

- the adverse event resolves or the symptoms or signs that constitute the adverse event return to baseline or is stable in the opinion of the investigator;
- there is a satisfactory explanation other than the study therapy for the changes observed; or
- death.

7.1.1 Definitions

An adverse event is defined as any untoward or unfavorable medical occurrence in a human research study participant, including any abnormal sign (for example, abnormal physical exam, imaging finding or clinically significant laboratory finding), symptom, clinical event, or disease, temporarily associated with the subject's participation in the research, whether or not it is considered related to the subject's participation in the research.

Adverse events encompass clinical, physical and psychological harms. Adverse events occur most commonly in the context of biomedical research, although on occasion, they can occur in the context of social and behavioral research. Adverse events may be expected or unexpected.

Acute Adverse Events

Adverse events occurring in the time period from the signing of the informed consent, through 90 days post treatment will be considered acute adverse events.

Late Adverse Events

Adverse events occurring in the time period from the end of acute monitoring, to 1 year post treatment, will be defined as late adverse events. In addition, the study team will review encounters in a select specialty category relevant to study endpoints. These select specialties include hospitalizations, medical oncology, radiation oncology, and urology records and will be limited in scope based on categorization of events (GU/GI) and also the type of records that will be queried (hospitalizations, medical oncology, and radiation oncology).

Severity

Adverse events will be graded by a numerical score according to the defined NCI Common Terminology Criteria for Adverse Events (NCI CTCAE) Version 5.0. Adverse events not specifically defined in the NCI CTCAE will be scored on the Adverse Event log according to the general guidelines provided by the NCI CTCAE and as outlined below.

- Grade 1: Mild
- Grade 2: Moderate
- Grade 3: Severe or medically significant but not immediately life threatening
- Grade 4: Life threatening consequences
- Grade 5: Death related to the adverse event

Serious Adverse Events

OHRP and the UTSW IRB define serious adverse events as those events, occurring at any dose, which meets any of the following criteria:

- Results in death
- Is life-threatening (places the subject at immediate risk of death from the event as it occurred);
- Results in inpatient hospitalization^{1,2} or prolongation of existing hospitalization
- Results in persistent or significant disability/incapacity
- Results in a congenital anomaly/birth defect
- Based upon appropriate medical judgment, may jeopardize the subject's health and may require medical or surgical intervention to prevent one of the other outcomes listed in this definition.

Note: A "Serious adverse event" is by definition an event that meets **any** of the above criteria. Serious adverse events may or may not be related to the research project. A serious adverse event determination does not require the event to be related to the research. That is, both events completely unrelated to the condition under study and events that are expected in the context of the condition under study may be serious adverse events, independent of relatedness to the study itself. As examples, a car accident requiring >24 hour inpatient admission to the hospital would be a serious adverse event for any research participant; likewise, in a study investigating end-stage cancer care, any hospitalization or death which occurs during the protocol-specified period of monitoring for adverse and serious adverse events would be a serious adverse event, even if the event observed is a primary clinical endpoint of the study.

¹Pre-planned hospitalizations or elective surgeries are not considered SAEs. Note: If events occur during a pre-planned hospitalization or surgery, that prolong the existing hospitalization, those events should be evaluated and/or reported as SAEs.

² NCI defines hospitalization for expedited AE reporting purposes as an inpatient hospital stay equal to or greater than 24 hours. Hospitalization is used as an indicator of the seriousness of the adverse event and should only be used for situations where the AE truly fits this definition and NOT for hospitalizations associated with less serious events. For example: a hospital visit where a patient is admitted for observation or minor treatment (e.g. hydration) and released in less than 24 hours. Furthermore, hospitalization for pharmacokinetic sampling is not an AE and therefore is not to be reported either as a routine AE or in an expedited report.

7.1.2 Unanticipated Problems Involving Risks to Subjects or Others (UPIRSOs):

The phrase "unanticipated problems involving risks to subjects or others" is found, but not defined in the HHS regulations at 45 CFR 46, and the FDA regulations at 21 CFR 56.108(b)(1) and 21 CFR 312.66. For device studies, part 812 uses the term unanticipated adverse device effect, which is defined in 21 CFR 812.3(s). Guidance from the regulatory agencies considers unanticipated problems to include any incident, experience, or outcome that meets ALL three (3) of the following criteria:

- Unexpected in terms of nature, severity or frequency given (a) the research procedures that are described in the protocol-related documents, such as the IRB-approved research protocol and informed consent document; and (b) the characteristics of the subject population being studied;

AND

- Related or possibly related to participation in the research (possibly related means there is a reasonable possibility that the incident, experience, or outcome may have been caused by the procedures involved in the research);
AND
- Suggests that the research places subjects or others at greater risk of harm (including physical, psychological, economic, or social harm) than was previously known or recognized. Note: According to OHRP, if the adverse event is serious, it would always suggest a greater risk of harm.

Follow-up

All adverse events will be followed up according to good medical practices.

7.2 Steps to Determine If a Serious Adverse Event Requires Expedited Reporting to the SCCC DSMC and/or HRPP

Step 1: Identify the type of adverse event using the NCI Common Terminology Criteria for Adverse Events (CTCAE v5).

Step 2: Grade the adverse event using the NCI CTCAE v5.

Step 3: Determine whether the adverse event is related to the protocol therapy.

Attribution categories are as follows:

- Definite – The AE *is clearly related* to the study treatment.
- Probable – The AE *is likely related* to the study treatment.
- Possible – The AE *may be related* to the study treatment.
- Unlikely – The AE *may NOT be related* to the study treatment.
- Unrelated – The AE *is clearly NOT related* to the study treatment.

Note: This includes all events that occur up to the end of the acute adverse events reporting period as defined in section 7.1.1. Any event that occurs more than 30 days after the last dose of and is attributed (possibly, probably, or definitely) to the agent(s) must also be reported as indicated in the sections below.

Step 4: Determine the prior experience of the adverse event. Expected events are those that have been previously identified as resulting from administration of the treatment. An adverse event is considered unexpected, for expedited reporting purposes only, when either the type of event or the severity of the event is not listed in:

- the current known adverse events listed in the Agent Information Section of this protocol (if applicable);
- the drug package insert (if applicable);
- the current Investigator's Brochure (if applicable)
- the Study Agent(s)/Therapy(ies) Background and Associated Known Toxicities section of this protocol

7.2.1 Reporting SAEs and UPIRSOs to the Simmons Comprehensive Cancer Center (SCCC) Data Safety Monitoring Committee (DSMC)

SAEs and UPIRSOs at all sites, which occur in research subjects on protocols for which the SCCC is the DSMC of record, require reporting to the DSMC regardless of whether IRB reporting is required. ***All SAEs occurring during the protocol-specified monitoring period and all UPIRSOs should be submitted to the SCCC DSMC within 5 business days of the study team members awareness of the event(s).*** In addition, for participating centers other than UTSW, local IRB guidance should be followed for local reporting of serious adverse events or unanticipated problems.

The UTSW study PI is responsible for ensuring SAEs/UPIRSOs are submitted to the SCCC DSMC Coordinator. This may be facilitated by the IIT project manager, study team, subsite or other designee. Electronic versions of the eIRB Reportable Event report; FDA Form #3500A forms, or other sponsor forms, if applicable; and/or any other supporting documentation available should be submitted to the DSMC.

UT Southwestern and affiliates will submit documentation via the SAE submission portal. All subsites participating in multi-center study may utilize the Serious Adverse Event Template and submit to the IIT Project Manager, or designee. The DSMC Coordinator will route the form to the DSMC Chair who determines if immediate action is required. Follow-up eIRB reports, and all subsequent SAE or UPIRSO documentation that is available are also submitted to the DSMC Chair who determines if further action is required via the same process. (See *Appendix V of the SCCC DSMC Plan for instructions on how to submit SAEs through the portal and for a template Serious Adverse Event Form which may be utilized by subsites on multi-center IIT studies*).

If the event occurs on a multi-institutional clinical trial coordinated by the UTSW Simmons Comprehensive Cancer Center, the IIT Project Manager or designee ensures that all participating sites are notified of the event and resulting action, according to FDA guidance for expedited reporting. DSMC Chair reviews all SAEs and UPIRSOs upon receipt from the DSMC Coordinator. The DSMC Chair determines whether action is required and either takes action immediately, convenes a special DSMC session (physical or electronic), or defers the action until a regularly scheduled DSMC meeting.

Telephone reports to Urology CRO, [contact]
Written reports to:
UTSW SCCC Data Safety Monitoring Committee Coordinator Email: [contact] [contact] or deliver to BLB.306
UTSW Institutional Review Board (IRB) Submit a Reportable Event via eIRB with a copy of the final sponsor report as attached supporting documentation

Reporting Unanticipated Problems Involving Risks to Subjects or Others (UPIRSOs) to the UTSW HRPP

UTSW reportable event guidance applies to all research conducted by or on behalf of UT Southwestern, its affiliates, and investigators, sites, or institutions relying on the UT Southwestern IRB. Additional reporting requirements apply for research relying on a non-UT Southwestern IRB.

According to UTSW HRPP/IRB policy, UPIRSOs are incidents, experiences, outcomes, etc. that meet **ALL three (3)** of the following criteria:

1. Unexpected in nature, frequency, or severity (i.e., generally not expected in a subject's underlying condition or not expected as a risk of the study; therefore, not included in the investigator's brochure, protocol, or informed consent document), AND
2. Probably or definitely related to participation in the research, AND
3. Suggests that the research places subjects or others at a greater risk of harm (including physical, psychological, economic, or social harm) than was previously known or recognized. Note: According to OHRP, if the adverse event is serious, it would always suggest a greater risk of harm.

For purposes of this policy, UPIRSOs include unanticipated adverse device effects (UADEs) and death or serious injury related to a humanitarian use device (HUD).

UPIRSOs must be promptly reported to the UTSW HRPP within 5 working days of PI awareness.

Events NOT meeting UPIRSO criteria:

Events that do NOT meet UPIRSO criteria should be tracked, evaluated, summarized, and submitted to the UTSW HRPP/IRB at continuing review.

For more information on UTSW HRPP/IRB reportable event policy, see [policy_9.5reportable.pdf \(utsouthwestern.edu\)](https://utsouthwestern.edu/policy_9.5reportable.pdf)

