1.3 Immune Checkpoint Inhibitor Therapy

Immune checkpoint inhibitor (ICI) therapy has assumed increasing importance in the management of bladder cancer. ICI agents function to nonspecifically stimulate the patient's immune response and decrease tumor immune evasion by inhibiting negative regulators of the immune response. In bladder cancer, most interest has attached to monoclonal antibodies which block the immunosuppressive surface receptor PD-1 or its ligand PD-L1²⁵.

Three PD-1 or PD-L1 inhibitors (avelumab, nivolumab, and pembrolizumab) are FDA-approved for second-line use in platinum-refractory advanced bladder cancer, based on clinical trials which showed objective response rates of 15-20%²⁶⁻³⁰. Two agents (atezolizumab and pembrolizumab) are FDA-approved for first-line use in patients who are ineligible for platinum-based chemotherapy, based on clinical trials showing objective response rates of 25-30% in this setting^{31,32}. Finally, avelumab has recently gained FDA approval for use as maintenance therapy following initial response to chemotherapy in advanced/metastatic bladder cancer, with clinical trials demonstrating an improvement in median overall survival from 14 to 21 months³³.

More recent efforts have explored a role for ICI treatments in the neoadjuvant setting. Two clinical trials, ABACUS and PURE-01, explored the use of neoadjuvant atezolizumab and pembrolizumab respectively, and reported pathologic complete response (pCR, meaning ypT0 N0) rates of 31% and 37%, respectively^{34,35}. While several other ongoing trials exist in this space, only a single trial has enrolled significant numbers of patients with clinical node-positive disease. In this trial, NABUCCO, patients with cN+ disease represented 42% of total enrollment. Neoadjuvant treatment with dual ICI agents (the PD-1 inhibitor nivolumab and the CTLA-4 blocker ipilimumab) resulted in an overall pCR rate of 46%³⁶.

Given their widespread clinical use in bladder and other malignancies, the adverse effect profile of ICI agents is well characterized. In the second-line trials cited above, for example, grade ≥ 3 adverse events occurred in 5-18% of patients and most notably

included autoimmune reactions at various sites including pneumonitis, colitis, and hepatitis²⁶⁻³⁰.

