4.11 Duration of Follow Up

All follow up after radical cystectomy represents the standard of care. Patients will be followed for adverse outcomes for 90 days following radical cystectomy. After that point, subjects will only be followed for progression-free and overall survival for two years from the date of first PULSAR treatment or disease recurrence, whichever occurs first.

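### The only active search for late adverse events is limited to GU/GI, so late immune-related events elsewhere, such as pneumonitis, are not actively sought

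*Combined protocol and SAP*

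**What the plan says.** Section 7.1.1 divides adverse events by time. Those arising "from the signing of the informed consent, through 90 days post treatment will be considered acute adverse events". For the rest of the year: "Adverse events occurring in the time period from the end of acute monitoring, to 1 year post treatment, will be defined as late adverse events". Neither definition names an organ system.

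The late paragraph then continues: "In addition, the study team will review encounters in a select specialty category relevant to study endpoints". This review is "limited in scope based on categorization of events (GU/GI", and also by "the type of records that will be queried (hospitalizations, medical oncology, and radiation oncology".

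The follow-up sections describe less. Section 4.11 follows patients for adverse outcomes until 90 days after cystectomy, after which "subjects will only be followed for progression-free and overall survival for two years". The six-monthly contact in 5.2.5 is for recurrence and vital status. In the 5.4 table, the toxicity row is blank in the six-monthly column.

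Section 1.3 reports Grade 3 or higher adverse events in 5-18% of patients in the second-line checkpoint inhibitor trials, and says that these most notably "included autoimmune reactions at various sites including pneumonitis, colitis, and hepatitis". Section 4.8 allows the inhibitor to continue beyond the study period at the treating oncologist's discretion.

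**The concern.** The protocol summary makes safety of PULSAR in patients on a checkpoint inhibitor a stated objective. During treatment and up to the 90-day post-cystectomy visit, toxicity is assessed at scheduled visits for any CTCAE term. After that visit, the one procedure that would find events is confined to GU/GI. Of the three immune reactions named in 1.3, colitis is a GI event, hepatitis is one only on a broad reading, and pneumonitis is not one. Exposure to the inhibitor may continue through this period.

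Two things are at stake. A late immune-related event outside GU/GI may go unrecorded. And a statement that the combination has little late toxicity would be supported by active ascertainment for GU/GI only, while the acute figures beside it rest on all organ systems.

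**Working it through.** The plan gives no late event rate or target, so there is no figure to reproduce. The check compares the collection procedures and measures the time they leave uncovered.

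**Inputs.** Trial therapy ends at the third fraction (4.10). Cystectomy follows 4-8 weeks later, or 28-56 days (4.1). The last toxicity visit is 90 days after cystectomy (5.2.4), with a window of ±4 weeks (5.3). The acute period ends 90 days after treatment and the late period ends at 1 year (7.1.1). Fractions are 12-16 days apart (5.4).

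**Late window, if treatment ends at the third fraction.** 365 − 90 = 275 days.

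**Last toxicity visit, in days after the third fraction.** Nominal: 28 + 90 = 118 to 56 + 90 = 146.

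**Late days after that visit.** 365 − 146 = 219 to 365 − 118 = 247. As a share, 219/275 = 80% and 247/275 = 90%. With the ±4-week window the visit can fall from day 28 + 62 = 90 to day 56 + 118 = 174, so the remainder can run from 365 − 174 = 191 to 365 − 90 = 275 days.

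**If post treatment is instead counted from cystectomy.** The acute period ends at the nominal date of the last visit, and all 275 late days follow it.

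**Patients without surgery.** The 30- and 90-day visits are dated from cystectomy. At the completion rates of 60% and 90% in 9.2, non-completers number 27 × 0.40 = 10.8 to 27 × 0.10 = 2.7, so about 3 to 11 patients. This is an upper limit on those without surgery, because a cystectomy after sixteen weeks also counts as non-completion.

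**Sources of late events, side by side.**

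| Source | Finds events actively? | Organ scope |
|---|---|---|
| 90-day post-cystectomy visit | Yes, once | Any |
| Record review, 7.1.1 | Yes | GU/GI |
| Six-monthly contact, 5.2.5 | No toxicity item | None |
| Reporting note, 7.2 | No, applies once an event is known | Any |

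**Illustration of size.** Only the 5-18% comes from the documents, and it describes second-line inhibitor trials. Assume that 10-50% of such events are both late and outside GU/GI. The expected number among 27 patients is then 27 × 0.05 × 0.10 = 0.14 to 27 × 0.18 × 0.50 = 2.43. The chance of at least one is 1 − (1 − 0.005)^27 = 13% to 1 − (1 − 0.09)^27 = 92%. The width of this range shows that the documents do not fix the size.

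**The case against.** The strongest reply is textual. The late definition has no organ limit, and the GU/GI restriction belongs to a review introduced as an addition. A reader might infer that the plan counts only GU/GI events as late toxicity, that pneumonitis drops out by construction, or that coverage outside GU/GI is zero. The documents do not support any of these. The 7.2 note requires reporting of known events beyond 30 days that are even possibly attributed to the agent(s), whatever the organ. Section 7.2.1 sends every serious event in the monitoring period to the safety committee. Colitis stays in scope. The 90-day post-cystectomy visit has no organ limit and can fall inside the late window.

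A reader might also infer that late rates will look lower than acute rates. That is not established. Section 9.3 plans no such comparison. The acute window is 24 + 90 = 114 to 32 + 90 = 122 days from the first fraction, against 275 late days, and it contains the radiation. The direction of any difference cannot be put down to the GU/GI limit.

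Finally, the inhibitor is standard of care with a known profile, and the added radiation is to the bladder and pelvic nodes, so a GU/GI focus is a defensible choice for a supplementary review.

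All of this narrows the point without removing it. A definition and a reporting duty do not find events. After the last visit, the GU/GI review is the only active source described. The agent's name is missing from the available text of the 7.2 note, so no weight is placed on that gap, but the text does not settle whether an event attributed to the inhibitor alone would qualify.

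**Conclusion.** The concern holds in limited form. Late events are defined for all organ systems but actively sought only for GU/GI once the 90-day post-cystectomy visit has passed. That leaves 219-247 of 275 late days (80-90%) without a scheduled toxicity evaluation, on nominal visit timing and with treatment ending at the third fraction. Patients who never have surgery lack that visit altogether. Late immune-related events outside GU/GI would be captured only if noticed and reported, and acute and late rates rest on different ascertainment.

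The number of events missed is not derivable, since any split by timing or organ is an assumption. Neither the primary endpoint nor the sample size is affected. The change is worth making because it is cheap and serves a stated safety objective.

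**What to change.** In 7.1.1, state that the late record review covers GU and GI events of any grade, as now, plus immune-related events of any organ system. The hospitalization and medical oncology records already queried can supply these.

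In the same edit:

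- Say whether any organ limit applies to late adverse events as a whole or only to the added review.
- Reconcile 4.11 and 5.2.5 with the one-year late window.
- State what post treatment is counted from: 4.10 ends therapy at the third fraction, while 4.11 counts from cystectomy.
- Reconcile the two lists in 7.1.1: urology is among the specialties but not among the record types queried.
- Say how the late window applies to patients who never have surgery.

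If the GU/GI limit is kept, report acute rates on the same GU/GI set beside the late rates, and state that late toxicity outside GU/GI was not systematically assessed.

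The cost is a few sentences and modest extra abstraction, with no added visits or procedures.
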